## **4.3 Study Outcome Measures**

All patients enrolled in the study and do not have a renal transplant, will be included in these outcome measurements unless otherwise noted.

**Primary Patency:** The interval from the time of access placement until any intervention designed to maintain or re-establish patency, access thrombosis, access abandonment, or the time of measurement of patency.

❖ **endoAVF abandonment definition:**

The endoAVF is considered abandoned if any of the following occur:

- The endoAVF is occluded and patency cannot be restored by any intervention, including medical, surgical, radiological or rest through the last follow up;
- The endoAVF is deemed inadequate for dialysis (for example, it never matures or is too deep for needle access) and the associated problem cannot be corrected by any intervention, including medical, surgical, radiological or rest;
- The endoAVF is ligated.

An endoAVF is not considered abandoned when it is not cannulated in subjects with a successful renal transplantation or when reasons of subject preference alone preclude cannulation.

**Assisted Primary Patency:** The interval from access placement to thrombosis or abandonment; not triggered by access circuit interventions performed in the absence of occlusion.

**Secondary Patency:** The interval from the time of access placement until access abandonment, loss to thrombosis, or the time of patency measurement including intervening manipulations (surgical or endovascular interventions) designed to re-establish functionality in thrombosed access.

**Functional Patency:** The interval of time from the first 2-needle dialysis utilizing the access until access abandonment.

**Procedure Success:** The successful creation of an endoAVF with blood flow confirmed intraoperatively by fistulography or by duplex ultrasound postoperatively.

**Time to Endovascular Fistula (endoAVF) Maturation (Vascular Access Usability):** Total time (number of days) from successful endoAVF creation to one of the following:

- Successful hemodialysis using 2 needle cannulation ***OR***
- Vascular accesses that is free of stenosis or thrombosis, with brachial artery flow of at least 500 ml/min and at least a 4.0 mm vein diameter as measured via duplex ultrasound.

**Time to Cannulation:** The time (number of days) from the index procedure (successful endoAVF creation) to the first use of the endoAVF for cannulation will be reported.

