**Number of Patients Who Met Functional Cannulation:** Functional Cannulation is defined as 2-needle access of the endoAVF access circuit with performance of  $\geq 2/3$ rds of  $\geq 120$  minute dialysis sessions through the endoAVF access circuit over a continuous 28-day period.

**Central Venous Catheter (CVC) Exposure:** CVC exposure will be analyzed at the follow-up time points, presenting the number/percent of patients reporting CVC use and the number/percent reporting dialysis access through other means, as well as the number/percent of subjects not yet on dialysis.

**Adverse Events:** Rate of serious procedure or device related Adverse Events (AEs) throughout the study period. The relevant events and rates of occurrence will be analyzed with a time component, to analyze procedural AEs and post-procedural AEs.

**Intervention Rate:** The percentage of patients requiring intervention will be calculated at 3, 6 and 12 months follow-up visits post index procedure. The rate of interventions that occurred during the index procedure and during short term follow-up will also be calculated.

The endoAVF-related interventions include:

- Interventions to maintain or restore patency of the endoAVF, including endovascular and surgical procedures designed to address occlusive thrombosis (resulting in absence of thrill or bruit at endoAVF) and clinically significant occlusive stenosis at or near endoAVF site.
- Interventions to support maturation of the arterialized vein segments, including endovascular procedures such as secondary coil embolization to facilitate flow into the target cannulation veins.
- Interventions to support cannulation of the arterialized vein segments, including procedures such as a superficialization or elevation where the target cannulation vein is brought closer to the skin surface to enable cannulation, without the creation of a new AV fistula.
- Any intervention to address any complications or adverse events of the access circuit.

**Note:** Any additional procedure performed at the time of the index procedure to address an adverse event will require a Post-Procedure Intervention eCRF to be completed.

**Note:** Diagnostic fistulogram, angiogram or duplex ultrasound will not be considered an intervention for the purpose of this study.

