## 6 ADVERSE EVENTS

An Adverse event (AE) will be defined as any adverse medical change (i.e., *de novo* or increased severity in a preexisting condition) from the patient's baseline condition that occurs during the course of the clinical study, after starting treatment, whether considered treatment-related or not. "Treatment" includes all commercially-approved products administered according to the study protocol and specific Instruction for use (IFU) documents.

Any pre-planned procedures (refer to Section 4.5.3- 2nd-Stage Procedures), or additional interventions, will not be considered AEs for this study. In addition, normally expected symptoms caused by the treatment that do not prolong or affect patient discharge, or are managed with observation alone and do not require intervention (e.g., medical, endovascular, surgical) are not considered an AE for this study.

These may include but are not limited to:

- Transient arterial spasm resolving spontaneously OR with medication only
- Minor discomfort or bruise at the arterial access site
- Small amount of bleeding at point of arterial access
- Transient numbness, tingling or coolness that resolved within 4 weeks post index procedure
- Bruising at the AVF creation site
- Side effects of standard-of-care medications
- Hematoma at the arterial and/or venous access site(s) and did not require endovascular or surgical intervention nor adversely affected discharge.

Only AEs that are relevant to index procedure, study device, access site or the endoAVF will be collected in the study. For example, if the subject has knee replacement or undergoes a hysterectomy, these events will be considered as non-study related and will not be required to be recorded via Adverse Event eCRF.

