**Table 6-1: Adverse Event Type**

AE Type	Definition
Serious Adverse Event (SAE)	AE that: 

• led to death,

• led to serious deterioration in the health of the patient, that either resulted in:

◦ a life-threatening illness or injury, or

◦ a permanent impairment of a body structure or a body function, or

◦ in-patient or prolonged hospitalization, or

◦ medical or surgical intervention to prevent life-threatening illness or injury or permanent impairment to a body structure or a body function,

• led to fetal distress, fetal death or a congenital abnormality or birth defect

Adverse Device Effect (ADE)	AE related to the use of study device.  NOTE: This definition includes adverse events resulting from insufficient or inadequate IFU, deployment, installation, operation, or any malfunction of the study device. In addition to any event resulting from use error or from intentional misuse of the study device.

Serious ADE (SADE)	ADE that has resulted in any of the consequences characteristic of a SAE.
Unanticipated SADE (USADE)	USADE which by its nature, incidence, severity or outcome has not been identified in the current version of the study protocol, IFU, or other study documentation.

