## **6.1 Relationship to Device or Procedure**

The Investigator will also evaluate the relationship of the adverse event to the everlinQ endoAVF System or procedure according to the following definitions:

**Definite (YES):** The AE follows a reasonable timing from treatment (or attempted treatment) with the device and the possibilities of factors other than the device or the index procedure, such as underlying disease, concomitant drugs, or concurrent treatment can be excluded. This includes an AE that occurs during the index (endoAVF creation) procedure.

**Probable (YES):** The AE follows a reasonable timing from treatment (or attempted treatment) with the device and the probability of device or procedure involvement cannot be excluded. However, other factors such as underlying disease, concomitant medications, or concurrent treatment may be possible.

**Unlikely (NO):** The AE follows an unlikely timing relationship from treatment (or attempted treatment) or is more likely due to other factors and there is no definitive information suggesting that it was related to the device or procedure.

**Not Related (NO):** The AE has no timing relationship from treatment (or attempted treatment) or it can be explained by other factors, including underlying disease, concomitant medication, or concurrent treatment.

The Investigator will evaluate the relationship to the everlinQ device portion of the procedure using the yes/no definitions above. The everlinQ device portion of the procedure only includes insertion, deployment and removal of the everlinQ catheters.

All reported adverse events will be reviewed and adjudicated by an independent Clinical Events Committee (CEC).

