## **7 DATA ANALYSIS**

The study will be observational in nature and will not involve the formulation or statistical testing of study hypotheses.

Variables that are categorical in nature (such as gender) will be summarized by frequencies and percentages while those that are continuous in nature (such as age) will be summarized by the mean, standard deviation, minimum and maximum values. Continuous variables that appear not to be normal in distribution will also be described by the median value.

Variables involving time (such as primary patency) will be analyzed using the Kaplan-Meier product limit approach. This approach yields cumulative probabilities of having an endoAVF for a given period of time without the occurrence of some specified terminal event, such as endoAVF thrombosis. The analysis requires both a time variable and a variable indicating whether or not the event of interest has occurred. Results of these analyses will be presented both graphically and in tabular form.

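### The only adverse-event rate the protocol defines is confined to serious related events in patients without a renal transplant, although relevant events of any seriousness are collected and adjudicated

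*Combined protocol and SAP*

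**What the plan says.** The Adverse Events entry in Section 4.3 (Study Outcome Measures) has two sentences. The first sets the outcome: "Rate of serious procedure or device related Adverse Events (AEs) throughout the study period". The second adds timing: "The relevant events and rates of occurrence will be analyzed with a time component", meaning a division into procedural and post-procedural events. The protocol summary lists adverse events as an outcome with no definition and no limit on seriousness.

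Section 4.3 opens with a rule for all its outcomes: "All patients enrolled in the study and do not have a renal transplant, will be included in these outcome measurements unless otherwise noted". The Adverse Events entry notes no exception.

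Collection is set in Section 6: "Only AEs that are relevant to index procedure, study device, access site or the endoAVF will be collected in the study". The filter there is relevance, not seriousness. Section 6 also removes normally expected symptoms, including those that "are managed with observation alone and do not require intervention". Table 6-1 sets the criteria for a serious event, among them "medical or surgical intervention to prevent life-threatening illness or injury or permanent impairment to a body structure or a body function". Section 6.1 codes relationship as yes (definite, probable) or no (unlikely, not related) and sends every reported event to the independent CEC.

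Section 7 specifies no adverse-event table. Its general rule is that categorical variables "will be summarized by frequencies and percentages".

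**The concern.** The study tests no hypothesis, so its reported rates are its product. Section 4.2 says the data may support reimbursement and publications. If the one defined adverse-event rate covers serious related events only, it supports a statement about those events and nothing wider. It does not describe non-serious access-site and fistula events, although sites report them and the CEC reviews them. Whether such events appear in a report would be decided later, when the results are known.

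The transplant rule adds a second restriction. It suits patency, where a transplant removes the need for the access. For safety it removes a patient because of something that happens after treatment. A serious event on the day of the index procedure would leave the rate if that patient later received a transplant during follow-up.

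**Working it through.** The plan states no adverse-event rate, so there is no figure to reproduce. The check compares scope at each stage.

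| Stage | Place | Seriousness limit | Relationship or relevance limit | Transplant patients |
|---|---|---|---|---|
| Outcome label | Protocol summary | none | none | not mentioned |
| Collection | Section 6 | none | relevant to procedure, device, access site or fistula | kept |
| Adjudication | Sections 6.1 and 8.3 | none | none beyond being reported | kept |
| Defined rate | Section 4.3 | serious | procedure or device related | left out |

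**Step 1. Is any event collected but not counted?** It must survive the Section 6 carve-out, meet no Table 6-1 criterion and be coded yes for relationship. Table 6-1 defines the adverse device effect separately from its serious subset, so the protocol itself recognises a non-serious device effect. As an example, take numbness in the hand that lasts beyond the four weeks named in the carve-out, is treated with medication, needs no hospital stay and is judged probable. If the treatment was not given to prevent permanent impairment, the event is reported and adjudicated and adds 0 to the defined rate.

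**Step 2. Does another outcome count it?** The Intervention Rate in Section 4.3 includes interventions for complications or adverse events of the access circuit, as a percentage of patients at 3, 6 and 12 months. An event that led to such an intervention is counted there, but as an intervention, with no event type and no adjudicated relationship. Thrombosis and abandonment enter the patency outcomes. A related non-serious event outside these routes enters no specified rate.

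**Step 3. What does the transplant rule do?** Let N be the number enrolled and T the number left out for transplant. Let a be the proportion with a qualifying event among the N − T kept, and b the proportion among the T left out.

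- Rate as written: a
- Rate in all enrolled: [(N − T)·a + T·b] / N
- Difference, all enrolled minus as written: (T/N)·(b − a)

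The documents cap enrolment at 200 and give no value for T, a or b. Neither the size nor the direction of the difference can therefore be stated. It is zero only if T = 0 or a = b.

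**Step 4. Does Section 7 fill the gap?** Its rule for categorical variables allows a table of non-serious events but does not call for one. For interventions, by contrast, the Definitions table commits to reporting the rate of all interventions and of specific ones. Adverse events have no equivalent commitment.

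**The case against.** The strongest reply is that Section 4.3 may be wider than it first looks. Its second sentence speaks of relevant events without repeating the seriousness limit, and relevance is the test Section 6 uses for the whole collected set. The summary's unqualified label points the same way. The adjective in the first sentence could also be attached to procedure-related events alone. These readings are possible, but the text does not state them. The second sentence follows directly on the serious related definition and most naturally adds a timing split to it. If the wider reading is intended, one sentence would settle it.

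A second reply is that the uncounted group is small. Part of this stands. Section 6 removes expected symptoms that are only observed, Table 6-1 makes hospitalised events and treatment to prevent permanent impairment serious, and the Intervention Rate picks up events that led to an access-circuit intervention. This narrows the gap but does not close it.

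A third reply is that serious related events are a legitimate headline and that no test, sample size or success criterion depends on them. That stands, and it limits the weight of the point.

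A reader might go further and infer that non-serious events will be lost or withheld. The documents do not support that: the events are recorded, the CEC adjudicates them, and nothing bars tabulating them. Nor do they support the inference that steal or hand ischaemia escapes the rate. Such an event counts when it is serious and related, and the protocol defines no separate steal event on which to base a required row.

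**Conclusion.** The point holds as a matter of definition. On the natural reading of Section 4.3, a related non-serious event enters no specified adverse-event rate, and renal-transplant patients are left out of the rate that is specified. Two assumptions carry this: that the second sentence of the entry does not widen the first, and that the transplant rule applies to adverse events because no exception is written.

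The effect in patients cannot be estimated, since the documents give no frequency of non-serious events or of transplants. Counting the categories that lack a rate would not measure it either. A reader might infer that the transplant rule flatters the safety rate. The direction is unknown, because patients who receive a transplant could have more or fewer events than the rest. What can be said is that the rule selects on a post-treatment event, which a safety denominator should not do. This is a cheap improvement to a descriptive study, not a flaw that undermines it.

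**What to change.** Amend the Adverse Events entry in Section 4.3 in three ways:

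1. Keep the serious procedure- or device-related rate as the headline row.
2. Add the number and percentage of patients with at least one CEC-adjudicated event, by seriousness and by relationship (yes/no), with the existing procedural and post-procedural split.
3. Use all enrolled patients as the denominator for every adverse-event row, including the headline row, and write this as an explicit exception to the section's transplant rule.

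The cost is a few sentences and a longer table, built from events already collected and adjudicated, with no new visit or test. There are two downsides. The any-seriousness figure will look less favourable than the serious related one, and the adverse-event denominator will differ from that of the other Section 4.3 outcomes, so the tables should label it.

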#### **4.4 Site Selection**

Investigational sites selected to participate in this clinical study will be dependent on the Investigator at the site having the necessary resources to fulfill the clinical research requirements outlined in the protocol. These resources include adequate patient population, facilities and support staff to perform the clinical evaluation according to all applicable requirements. Sites must reside in a region or country where the System is available for use and properly registered or licensed (i.e. CE Mark, Health Canada License).

## **4.5 Study Population**

Candidates for this trial are patients being evaluated for placement of vascular access for chronic hemodialysis. Only patients meeting all of the inclusion and none of the exclusion criteria who signed the Informed Consent Form (ICF) may be considered for participation.

### **4.5.1 Inclusion Criteria**

1. Adult (age >18 years old)
2. Currently on chronic dialysis or expected to be started on chronic dialysis within 3 months of planned endoAVF creation. Target treatment vein diameter(s) for fistula creation  $\geq$  2.0 mm as measured via Duplex Ultrasound or Venogram
3. Target treatment artery diameter(s) for fistula creation  $\geq$  2.0 mm as measured via Duplex Ultrasound or Arteriogram
4. Both radial and ulnar artery flow to the hand, as confirmed with Duplex Ultrasound and/or Allen's test (i.e.: palmar arch)

### **4.5.2 Exclusion Criteria**

1. Known central venous stenosis or central vein narrowing  $>$  50% based on imaging on the same side as the planned AVF creation
2. Absence of perforator feeding the target cannulation vein(s) via Venogram
3. Occlusion or stenosis  $>$  50% of target cannulation cephalic or basilic vein
4. Target cannulation vein that is  $<$  2.5 mm in diameter
5. Significantly compromised ( $\geq$  50% stenosis) flow in the treatment arm as determined by physician and imaging  
NOTE: patients that have  $\geq$  50% arterial stenosis may undergo a Digital Brachial Index (DBI) test, if DBI result is  $<$  .65 patient is excluded
6. Documented ejection fraction (EF)  $\leq$  35% in the last 6 months
7. Pregnant women
8. New York Heart Association (NYHA) class III or IV heart failure
9. Hypercoagulable state
10. Known bleeding diathesis
11. Documented history of drug abuse including intravenous drugs within six months of AVF creation
12. "Planned" concomitant major surgical procedure within 6 months of enrollment or previous major surgery within 30 days of enrollment
13. Known allergy to contrast dye which cannot be adequately pre-medicated
14. Known adverse effects to sedation and/or anesthesia which cannot be adequately pre-medicated
15. Evidence of active infections on the day of the index procedure
16. Estimated life expectancy  $<$  1 year
17. Patient is not willing to provide written informed consent, is not geographically stable and/or not willing to comply with required follow-up
18. Patient with a target cannulation vein that is  $>$  6 mm deep that would require a transposition procedure, defined as the elevation of a target cannulation vein AND the creation of a new AV fistula
19. Patient is not willing to undergo a 2nd stage procedure as defined in Section 4.5.3 of this protocol

### 4.5.3 2nd-Stage Procedure

Study patients may require secondary procedure(s), also known as 2nd-stage procedures. These are procedures that are performed AFTER the endoAVF index procedure. Such procedures are considered interventions and require completion of the Post-Procedure Intervention eCRF. These procedures may include but are not limited to the following:

- Procedures to support maturation of the arterialized vein segments (i.e. secondary coil embolization);
- Procedures to support cannulation of the arterialized vein segments (i.e. elevation or superficialization of a target cannulation vein);
- Procedures to maintain or restore patency of the AVF (i.e. balloon angioplasty).

## 5 STUDY SCREENING AND FOLLOW-UP PROCEDURES

Patients are required to undergo a thorough screening evaluation prior to the index procedure and return for evaluations according to the study follow-up schedule. Table 5-1: Schedule of Study Procedures outlines the required testing and follow-up required for each study interval. Study data will be collected on electronic case report forms (eCRFs) provided by the Sponsor.

**Table 5-1: Schedule of Study Procedures**

Assessment	Screening	Index Procedure	Post Index Procedure				
			0-10 Days Visit 1	1 Month Visit 2	3 Month Visit 3	6 Month Visit 4	12 Month Visit 5
Compliance Window	-60 days	day 0	0-10 days	21-45 days		Anniversary date +14 days	
Informed Consent	X						
History, Physical Exam, Pregnancy Test	X						
Blood Pressure	X	X	X	X	X	X	X
HTN Medications	X	X	X	X	X	X	X
DUS Evaluation	X	X 	X	X	X	X	X
Angio/Venography		X					
Adverse Events		X	X	X	X	X	X
Allen's Test /Palmar Arch	X	X	X	X	X	X	X
Dialysis Access Data				X 	X 	X 	X 
QOL Questionnaire	X				X	X	X

 Recommended post-procedure to confirm absence of bleeding or hematoma formation

 All efforts by the site must be undertaken to provide this data to the sponsor, minimally over a continuous 28-day period.

